## 2.7. Study Procedures

### Research Design and Data Source

The research will be conducted using an analytical experimental quantitative design. The data source used in this research is primary data, collected while neonates are hospitalized at [name] General Hospital in Bandung, Indonesia and Bandung Kiwari Regional Hospital, Bandung, Indonesia.

### Study Protocol:

1. **Sampling Stage:** Sampling will be conducted in the NHCU and NICU wards of [name] General Hospital Bandung and Bandung Kiwari Regional Hospital Bandung.
2. **Informed Consent:** A verbal and written explanation of the entire study (informed consent) will be provided to the parents/guardians of the study subjects.
3. **Enrolment:** The parents/guardians of the study subjects who agree to the study procedures will then sign the consent form.
4. **Screening:** The researcher will conduct interviews to obtain general data, maternal history, and birth history to identify subjects who meet the inclusion and exclusion criteria.
5. **Blood Sample Collection:** Peripheral venous blood samples will be collected from the case and control subjects twice (on Day 0 and Day 7). Each collection will be approximately for the examination of Vitamin D levels (i.e., 25(OH)D), hematology, peripheral blood smear morphology, and CRP.
6. **Intervention:** The subject groups who can tolerate enteral feeding will receive Vitamin D3 supplementation of either 400 IU or 800 IU once daily for 7 days.
7. **Sample Processing:** Blood samples will be sent to the Clinical Pathology Laboratory at [name] General Hospital Bandung for sample preparation. The 25(OH)D level examination will utilize a stored biological material (SBM), which will be stored at a temperature of -80°C.

### **3 GENERAL STATISTICAL METHODOLOGY**

#### **3.1. Objectives of Analysis Plan**

This analysis plan covers the analysis of all objectives.

#### **3.2. Analysis Software**

Analysis will be conducted using the Statistical Product and Service Solution (SPSS) for Windows, version 27.0 (IBM Corp., Armonk, NY, USA).

#### **3.3. Definition of Baseline**

The baseline is taken as the measures and assessments recorded at day-0.

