## 2. STUDY SYNOPSIS

This will be a randomized, multi-centered clinical trial. Participants will include preterm neonates diagnosed with neonatal sepsis who are treated with antibiotics. All eligible patients with parental consent, who cannot tolerate enteral feed will be assigned as Group 1 (antibiotic only). All eligible patients with parental consent, who can tolerate enteral feed enrolled into the trial will be randomized into two treatment groups. Group 2 will receive vitamin D as adjuvant therapy (400 IU) for seven days. Group 3 will receive vitamin D as adjuvant therapy (800 IU) for seven days. Each patient will undergo clinical assessments and blood examination at the beginning and end of each treatment period.

Study assessments will include the sepsis score (Tollner score and sepsis prediction score) and C-reactive protein examination.

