### 2.1. Primary Objective

1. To determine the effect on the modified Tollner sepsis score among groups of preterm neonates with sepsis receiving adjuvant Vitamin D therapy at doses of 400 IU/day and 800 IU/day, compared to those receiving antibiotics alone.
2. To determine the effect on the Sepsis Prediction Score among groups of preterm neonates with sepsis receiving adjuvant Vitamin D therapy at doses of 400 IU/day and 800 IU/day, compared to those receiving antibiotics alone.

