### 2.2. Secondary Objectives

To determine the effect on C-reactive protein (CRP) levels among groups of preterm neonates with sepsis receiving adjuvant Vitamin D therapy at doses of 400 IU/day and 800 IU/day, compared to those receiving antibiotics alone.

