### 2.3.3 Inclusion criteria

The inclusion criteria for the case group in this study comprise neonates (aged 0–28 days or a maximum post-menstrual age of 42 weeks) with a gestational age of 28–36 weeks who are admitted to the neonatal high care unit (NHCU) and neonatal intensive care unit (NICU) of [name] General Hospital, Bandung, and Bandung Kiwari Regional Hospital, and meet the following criteria:

- Patients diagnosed with neonatal sepsis confirmed by blood or cerebrospinal fluid (CSF) culture, OR patients meeting the criteria for suspected sepsis based on a modified Tollner sepsis score of  $\geq 5$ , OR Sepsis Prediction Score  $\geq 3$ .
- Parents or legal guardians are willing to participate in the study and have signed the informed consent form.

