## 2.4. Design and Intervention

This study is an analytical experimental study with a randomized controlled trial (RCT) design. All samples that meet the inclusion and exclusion criteria will be enrolled as study subjects. Subject characteristics data will be obtained from the patient's medical records. This was an open-label trial due to the nature of the nutritional intervention (NPO vs. enteral).

Subjects were subsequently allocated into three groups:

- Group 1: Subjects requiring medical fasting (NPO) due to their clinical condition, who received antibiotics alone.
- Group 2: Subjects able to tolerate enteral nutrition, who received antibiotics plus Vitamin D3 supplementation of 400 IU once daily for 7 days.
- Group 3: Subjects able to tolerate enteral nutrition, who received antibiotics plus Vitamin D3 supplementation of 800 IU once daily for 7 days.

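### Day 0 is defined as baseline, but the plan commits to no use of the Day-0 sepsis scores or CRP, either in an outcome analysis or in the baseline table

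*Combined protocol and SAP*

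**What the plan says.** Section 3.3 defines baseline: "The baseline is taken as the measures and assessments recorded at day-0". The synopsis (Section 2) sets the timing, "Each patient will undergo clinical assessments and blood examination at the beginning and end of each treatment period", and the content, "Study assessments will include the sepsis score (Tollner score and sepsis prediction score) and C-reactive protein examination". Step 5 of the Study Protocol (Section 2.7) draws blood, including for CRP, on Day 0 and Day 7.

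The objectives are worded as effects. Section 2.1 begins "To determine the effect on the modified Tollner sepsis score among groups of preterm neonates with sepsis" and treats the Sepsis Prediction Score the same way; Section 2.2 has "To determine the effect on C-reactive protein (CRP) levels among groups of preterm neonates with sepsis". Each compares the two vitamin D doses with antibiotics alone. None names a time point, a change or an adjusted value.

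Section 3.1 claims that the analysis plan extends to every objective, but Sections 3 and 4 contain no outcome test or model. The one statement on the form of analysis is in Section 2.6, where the sample size rests on an unpaired comparison of a numeric measure between groups.

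The baseline table in Section 4.2 covers sex, age, gestational age, birth weight, respiratory support, and vitamin D level and status. It has no row for the Tollner score, the Sepsis Prediction Score or CRP.

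Section 2.4 describes the comparator: "Group 1: Subjects requiring medical fasting (NPO) due to their clinical condition, who received antibiotics alone". Section 3.4 defines the analysis set by reference to randomised participants.

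**The concern.** Two things are at stake.

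The first is the 400 v 800 IU contrast, the only one protected by randomisation. With 19 infants per group, a Day-0 covariate that is already collected can shorten the confidence interval. The plan does not commit to using it.

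The second is the set of comparisons that Sections 2.1 and 2.2 name, each against Group 1. Clinical condition decides who is in that group, so its Day-0 severity may differ from that of the fed infants. The planned baseline table would not show such a difference in the outcome measures. The plan also leaves open whether the effect is a Day-7 difference, a difference in change or a Day-0-adjusted difference. When groups start level, these three estimate the same thing; when they do not, the estimates diverge. In an open-label trial with the form unstated, the choice can be made after the data are seen.

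**Working it through.** **The plan's own figure.** Section 2.6 gives 19 per group, and 3 x 19 = 57 agrees with the stated total. It gives no effect size or SD, so 19 cannot be reproduced. It is used here only as the group size, and no power figure is claimed.

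**Are Day-0 values available?** For CRP, yes, from step 5 of the Study Protocol. For the scores it is an inference, but a strong one: the synopsis puts them among the assessments at the start and end of treatment, and Section 2.3.3 admits infants on a Tollner score of at least 5 or a Sepsis Prediction Score of at least 3, as alternatives to a positive culture.

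**Assumed inputs.** The documents give neither r, the within-group Day-0/Day-7 correlation, nor D, the Day-0 gap between Group 1 and a vitamin D group in Day-0 SDs. I take r = 0.3, 0.5 and 0.7, D = 0.5, two-sided 95% intervals and, for change scores, equal SDs at the two days.

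**Randomised contrast, ANCOVA against unadjusted Day-7.** The ratio of CI widths is

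sqrt(1 - r^2) x sqrt(1 + 1/34) x t(0.975, 35)/t(0.975, 36).

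The last two factors are 1.0146 x (2.0301/2.0281) = 1.0156, the cost of estimating the slope.

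- r = 0.3: 0.9539 x 1.0156 = 0.969, 3.1% narrower
- r = 0.5: 0.8660 x 1.0156 = 0.880, 12.0% narrower
- r = 0.7: 0.7141 x 1.0156 = 0.725, 27.5% narrower
- r = 0: 1.0156, 1.6% wider
- Break-even: r^2 = 1 - 1/1.0156^2, so r is about 0.175

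**Randomised contrast, ANCOVA against change score.** With equal SDs the change has variance 2(1 - r) in units of the Day-7 variance, so the ratio is sqrt((1 + r)/2) x 1.0156.

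- r = 0.3: 0.8062 x 1.0156 = 0.819, 18% narrower
- r = 0.5: 0.8660 x 1.0156 = 0.880, 12% narrower
- r = 0.7: 0.9220 x 1.0156 = 0.936, 6% narrower

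The gain over change score shrinks as r rises, the reverse of the gain over Day-7.

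**Comparison with Group 1.** The within-group slope is r x SD7/SD0. Unadjusted Day-7 minus ANCOVA is therefore slope x D x SD0 = r x D x SD7, whatever the SD ratio. With equal SDs, change score minus ANCOVA is -(1 - r) x D.

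| r | Day-7 minus ANCOVA (SD) | Change minus ANCOVA (SD) |
|---|---|---|
| 0.3 | +0.15 | -0.35 |
| 0.5 | +0.25 | -0.25 |
| 0.7 | +0.35 | -0.15 |

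The Day-7 and change-score estimates are D = 0.5 SD apart at every r. For example, suppose Group 1 starts 0.5 SD worse and ends 0.25 SD worse, with r = 0.5. The Day-7 comparison favours vitamin D by 0.25 SD, ANCOVA gives 0.25 - 0.25 = 0, and change score favours antibiotics alone by 0.5 - 0.25 = 0.25 SD. For scale, the half-width of an unadjusted two-group interval is 2.028 x sqrt(2/19) = 0.66 SD.

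**The case against.** **The root defect is wider.** No outcome analysis is specified at all, and non-use of Day-0 values is one consequence. That is true, and one new SAP section could repair both. But a section that merely named a test could still leave out the Day-0 values, and would not add the missing table rows.

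**The documents point to a before/after comparison.** Measuring at the start and end of treatment and defining a baseline both suggest one. This is a fair reading, which is why change score is costed above. Nothing commits to it, however.

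**The plan has chosen an unadjusted Day-7 test.** A reader might infer this from Section 2.6. The text does not support it: that section sizes the trial, names no time point or model, and a between-group comparison of changes would also be unpaired.

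**The precision gain may be small.** Entry by score threshold can lower r. As an illustration, cutting a normal Day-0 score at its median turns 0.3, 0.5 and 0.7 into 0.19, 0.33 and 0.51. The real cut is only partial, since culture or the other score also admits. This stands: against unadjusted Day-7 the gain could be 3% or less. Low r is, however, where change score does worst.

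**Adjustment cannot rescue the Group 1 comparison.** This stands in full. Treatment and feeding status coincide completely, and Section 2.3.4 excludes infants whose feeding status changes during the seven days. With non-randomised groups, ANCOVA and change score can legitimately disagree, and neither is clearly right. A reader might also infer that Group 1 will be sicker at Day 0. That is plausible, but the documents give no Day-0 figures, so D is hypothetical.

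**Conclusion.** The point holds as an omission that should be corrected. Day-0 values of all three outcomes are planned, or in the case of the scores very probably planned, but no analysis and no table is committed to using them.

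For the randomised contrast the loss is one of precision: about 3% to 27% of CI width if Day-7 values are compared unadjusted, and about 18% to 6% if changes are compared, over r from 0.3 to 0.7. For the Group 1 comparisons, an assumed 0.5 SD Day-0 gap puts the two simple estimates 0.5 SD apart, so the conclusion can depend on a choice left open.

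These sizes rest on assumed r and D, 19 per group and, for change score, equal SDs. The case for the three table rows and for fixing the form of analysis in advance does not depend on them. It does not follow that Day-0 adjustment would make the Group 1 comparison a valid estimate of the vitamin D effect.

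**What to change.** 1. Add Day-0 Tollner score, Sepsis Prediction Score and CRP, by group, to the baseline table in Section 4.2.
2. For each score, prespecify ANCOVA of the Day-7 value on group with the same score's Day-0 value as covariate, reporting adjusted differences and 95% CIs. Do the same for CRP on the log scale, with a stated rule for values below detection. Make this the analysis of the randomised 400 v 800 IU contrast, and state whether that contrast is an objective, since Sections 2.1 and 2.2 do not clearly name it.
3. Report the comparisons of each dose with Group 1 separately, labelled non-randomised, with Day-0-adjusted and change-score estimates side by side. State that neither can separate vitamin D from fasting status.
4. Reconcile Section 3.4, which includes only randomised participants, with the use of Group 1 as comparator.

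The cost is one SAP section, a decision on the status of the dose contrast, a clarified analysis set and three table rows. No new data are needed. The statistical downside for the randomised contrast is one degree of freedom, and a CI up to about 1.6% wider than unadjusted Day-7 if r is below about 0.175.

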#### **3.4. Definition of analysis populations**

Data from this study will be analysed as a per-protocol analysis. Data from all participants who are randomised will be included in the per-protocol analysis.

#### **3.5. Definitions related to Adverse Events (AEs)**

Other than standard adverse effects, the following specific adverse events will be reported:

- Gastrointestinal symptoms: diarrhoea, vomiting, bloating, increased abdominal circumference >2 cm
- Hypercalcemia

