### 2.3.4 Exclusion criteria

Participants meeting any of the following criteria will be excluded from the study:

- Patients with major congenital malformations, including anencephaly, encephalocele, holoprosencephaly, hydrocephalus, meningomyelocele, spina bifida, omphalocele, gastroschisis, or congenital heart disease.
- Patients who were initially able to tolerate enteral feeding but developed a medical condition requiring fasting (NPO/Nil Per Os) during the 7-day monitoring period.
- Patients who initially required fasting (due to a medical condition) but became able to tolerate enteral feeding during the 7-day monitoring period.

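### No safety population is defined and the exclusion rule conflicts with the analysis population, so gastrointestinal events that lead to fasting may drop out of the vitamin D arms

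*Combined protocol and SAP*

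**What the plan says.** Four parts of the combined protocol and SAP bear on this point.

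- **Section 3.5 (adverse events).** "Other than standard adverse effects, the following specific adverse events will be reported": first "Gastrointestinal symptoms: diarrhoea, vomiting, bloating, increased abdominal circumference >2 cm", then hypercalcaemia. It gives no population, collection window, comparator or table layout.
- **Section 2.3.4 (exclusion criteria).** Infants meeting any listed criterion are excluded from the study. One criterion is "Patients who were initially able to tolerate enteral feeding but developed a medical condition requiring fasting (NPO/Nil Per Os) during the 7-day monitoring period". The mirror-image criterion applies to infants fasting at the start: "Patients who initially required fasting (due to a medical condition) but became able to tolerate enteral feeding during the 7-day monitoring period".
- **Section 3.4 (analysis populations).** "Data from this study will be analysed as a per-protocol analysis". The next sentence brings every randomised participant into that analysis. No other population is defined.
- **Sections 2 and 2.4 (allocation).** "All eligible patients with parental consent, who can tolerate enteral feed enrolled into the trial will be randomized into two treatment groups", namely 400 IU and 800 IU. Group 1 is not randomised. It consists of "Subjects requiring medical fasting (NPO) due to their clinical condition, who received antibiotics alone".

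**The concern.** The fasting criterion in Section 2.3.4 cannot be known when an infant is allocated; it is met only after treatment has begun. Vomiting, bloating and a growing abdominal girth, three of the events that Section 3.5 wants reported, are plausible reasons for stopping feeds. Under this rule, an infant with a mild event stays in the study, and one whose event was serious enough to stop feeding leaves it. The selection therefore depends on the safety outcome itself.

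At stake is what the trial can say about tolerability in preterm infants at two doses. If the events that led to fasting are not counted, both doses may look better tolerated than they were. If the share of affected infants made NPO is similar at both doses, more infants are lost from the dose that causes more events, so a difference between doses also shrinks.

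A second problem is the reference group. A reader wanting to put the vitamin D event rates in context would look to Group 1, but those infants are not being fed and were placed there because of their clinical condition.

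**Working it through.** **1. Do the sections agree?** Take an infant randomised to 400 IU or 800 IU who vomits on Day 3 and is made NPO.

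| Rule | Consequence for this infant |
|---|---|
| Section 2.3.4 | Excluded from the study |
| Section 3.4, first sentence (per-protocol label) | Normally left out |
| Section 3.4, second sentence (everyone randomised) | Included |
| Section 3.5 | Event to be reported, but not stated among whom |

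The plan permits either treatment of this infant. Section 3.4 read literally also leaves out Group 1, which was never randomised.

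**2. Size of the loss if Section 2.3.4 governs.** Let p be the true proportion with a listed gastrointestinal event and f the share of those infants made NPO and removed. If no one is removed for another reason, the rate among those retained is

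p(1 − f) / (1 − pf).

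The documents give neither p nor f, so both are assumed. The only plan figure used is 19 infants per group (Section 2.6). With 4 of 19 affected:

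| Affected infants removed | Retained with event / retained | Reported rate |
|---|---|---|
| 0 | 4/19 | 21.1% |
| 1 | 3/18 | 16.7% |
| 2 | 2/17 | 11.8% |
| 3 | 1/16 | 6.3% |

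Over a wider range:

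| True p | f = 0.25 | f = 0.50 | f = 0.75 |
|---|---|---|---|
| 0.20 | 0.158 | 0.111 | 0.059 |
| 0.30 | 0.243 | 0.176 | 0.097 |

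At f = 0.50, the expected number of affected infants removed from the 38 in Groups 2 and 3 is 38 × 0.20 × 0.50 = 3.8, or 38 × 0.30 × 0.50 = 5.7.

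**3. If infants without a listed event are also made NPO.** Let g be the share of unaffected infants removed. The reported rate becomes p(1 − f) / [p(1 − f) + (1 − p)(1 − g)], which is below p whenever f exceeds g. For example, with 2 of the 4 affected and 3 of the 15 unaffected removed, it is 2/(2 + 12) = 14.3%. That is still below 21.1%, but closer to it than 11.8%.

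**4. Effect on the dose comparison.** Assume true rates of 0.10 and 0.30, a difference of 0.20. With the same f in both arms, the difference among those retained is 0.166 at f = 0.25 and 0.124 at f = 0.50.

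**5. Comparison with Group 1.** Suppose vitamin D has no effect on these events.

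| Assumed rate, fed | Assumed rate, fasting | Apparent difference, f = 0 | f = 0.50 |
|---|---|---|---|
| 0.30 | 0.10 | +0.200 | +0.076 |
| 0.20 | 0.40 | −0.200 | −0.289 |

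The sign depends on how feeding and illness affect the symptoms, which the documents do not tell us. Group 1 also loses the infants who recover enough to feed.

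**The case against.** The strongest reply is that Section 3.4 includes every randomised participant. On that reading the infant made NPO stays in, the reported rate equals the true rate, and 400 IU versus 800 IU remains a sound randomised comparison in fed infants. Section 3.5 does not tie adverse-event reporting to the per-protocol population, and nothing says that events in excluded infants go unreported. A reader might infer that these events are certain to be lost and that a planned safety table will understate harm. The documents do not support that: the only table shell is the baseline one in Section 4.2, and the loss depends on which section is followed. This stands, and it makes the point conditional.

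It does not remove the point. Section 2.3.4 excludes infants from the study, not merely from one analysis, so an infant who leaves before Day 7 may have no later adverse-event record to include. A team could follow that section and still be complying with the plan.

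It is also fair that no adverse-event comparison with Group 1 is planned. The objectives in Sections 2.1 and 2.2 compare groups on the two sepsis scores and CRP. The remark about Group 1 is therefore a caution about interpretation, not a fault in a stated analysis.

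Lastly, the fall from 21% to 6% is the steep end of the illustration, with three of four affected infants removed. A fasting condition also need not come from a listed symptom, which is why step 3 of the working allows for other removals.

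**Conclusion.** The point holds in conditional form. Sections 2.3.4 and 3.4 conflict, and no safety population resolves the conflict. If the exclusion is applied, the gastrointestinal event rate in Groups 2 and 3 is too low. With an assumed 4 of 19 affected, 21% is reported as 17%, 12% or 6% when 1, 2 or 3 of them are removed. This takes fasting to be more frequent among affected than unaffected infants, and assumes their events are dropped along with them. If all randomised infants are counted, there is no loss.

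A reader might also infer that the fasting control hides harm. That does not follow: comparison with Group 1 can exaggerate or conceal an effect, so it is simply uninformative for these events. Hypercalcaemia, also listed in Section 3.5, is not covered by this argument.

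**What to change.** 1. Reconcile Sections 2.3.4 and 3.4, so that the plan says plainly whether an infant whose feeding status changes within the 7 days stays in the analysis.
2. Add to Sections 3.4 and 3.5 a safety set, for example: *All infants who received at least one dose of vitamin D, and all Group 1 infants, with adverse events counted to Day 7 whatever the later feeding status or exclusion.*
3. Report, by dose, the number of infants who became NPO after starting vitamin D and the reason.
4. Present gastrointestinal events for 400 IU and 800 IU with exact confidence intervals, and list Group 1 descriptively only. A formal test between doses is optional: with 19 per arm and no losses, power for 10% versus 30% is only about 0.33.

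None of this changes a dose or a feeding decision. The cost is SAP wording and keeping adverse-event records to Day 7 for infants who become NPO and remain in hospital. The reported rates may look less favourable.
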